The Impact of the Attention Training Technique on Attention Control and High Worry

Study Protocol and Statistical Analysis Plan

NCT03216382

June 10, 2021

Study Protocol and Statistical Analysis Plan

NCT03216382

Protocol

- Phone screen to assess eligibility
- Visit 1: Baseline
 - Participants completed consent form, a demographic questionnaire, the GAD-Q-IV, MCQ-30, ACS, PSWQ-PW, SMQ, and the CESD-R.
 - Participants completed the dot-probe task, ANT, and breathing focus task.
 - Participants assigned to complete daily diary every evening, monitoring worry and attention.
- Week 1: Diary
 - Monitoring worry and attention at home every evening
- Visit 2: Preintervention (1 week after baseline)
 - Participants completed the MCQ-30, the ACS, the SMQ, and the PSWQ-PW.
 - Participants completed the dot-probe, ANT, and breathing focus task.
 - Participants randomly assigned to one of the two conditions: attention training or control.
 - Participants completed self-focused attention rating scale.

- Participants given rationale (same for both conditions).
- Participants listened to ATT or control recording.
- Participants recomplete the self-focused attention rating scale and the credibility and expectancy questionnaire.
- Participants asked to listen to assigned recording once per day over the follow week while continuing to monitor worry and attention.
- Week 2: Recording and Diary
 - Participants listened to assigned recording once per day and complete diary every evening.
 - Before and after recording, participants completed self-focused attention rating scale. Participants also asked at the end of listening to the recording to what percentage they focused on the recording.
- Visit 3: Postintervention (1 week after preintervention)
 - Participants completed the MCQ-30, the ACS, and the PSWQ-PW.
 - Participants completed the dot-probe, the ANT, and the breathing focus task.
 - Participants were debriefed about the goals and hypotheses of the study.
 - Those in the control condition were offered the opportunity to listen to the ATT recording in the lab.

Data Analysis Plan

Scores from the questionnaires, the ANT, dot-probe task, and breathing focus task were analyzed using a 3x2 repeated measures Oneway Analysis of Variance (ANOVA), with time as a

variable with three levels (visits 1, 2 and 3) and condition as a variable with two levels (ATT and Control). This was a pre-planned analysis.

Diary data were analyzed using hierarchical linear modelling. The proposed structure of the data included 2 levels, the first level representing the data across time points (i.e., an individual's responses over the course of the study), and the second level representing the participant's assigned condition (ATT vs. Control). A piecewise analysis of the data was conducted with a random intercept and fixed slopes. Linear multilevel models were run separately for each outcome variable. Predictor variables included condition, time (piece 1: baseline, or visit 1 to visit 2 and piece 2: intervention period, or visit 2 to visit 3), and an interaction between condition and time. Quadratic models were also run, in case change was not linear. This was a pre-planned analysis.

Only uncontrollability of worry and self-focused attention were analyzed. It was decided post-hoc that uncontrollability and intensity may be redundant, and thus uncontrollability was chosen due to perceived uncontrollability of worry being part of the diagnostic criteria of GAD. Further, minutes of worry and frequency of worry episodes were difficult to interpret, as there was huge variability in responses. Many participants reported that they found it very difficult to quantify their worry in this way and they were not confident in their responses.

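### Do the before/after ratings of self-focused attention need an analysis that the plan does not give?

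*Combined protocol and SAP*

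**What the plan says.** **Schedule.** At Visit 2: Preintervention, the order is: "Participants randomly assigned to one of the two conditions: attention training or control"; then "Participants completed self-focused attention rating scale"; then a rationale common to both conditions, the recording, and "Participants recomplete the self-focused attention rating scale and the credibility and expectancy questionnaire". In Week 2: Recording and Diary, "Before and after recording, participants completed self-focused attention rating scale". The scale is absent from the lists for Visit 1, Week 1 and Visit 3. Separately, the Week 1 diary entry reads "Monitoring worry and attention at home every evening", and the evening diary continues through Week 2.

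**Analyses.** The Data Analysis Plan gives two. Questionnaire and task scores go into a 3x2 repeated measures ANOVA whose time factor is a "variable with three levels (visits 1, 2 and 3"). Diary data go into a two-level model with a random intercept and fixed slopes. Its predictors are condition, "time (piece 1: baseline, or visit 1 to visit 2 and piece 2: intervention period, or visit 2 to visit 3"), and condition by time, and quadratic versions were also run. The diary account ends with the outcomes that were kept: "Only uncontrollability of worry and self-focused attention were analyzed".

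**The concern.** The rating scale is the only measure listed immediately before and immediately after a recording, so it is the natural source for a within-session comparison of ATT with control. It is listed at one of the three visits, so it cannot fill the ANOVA time factor. It has no ratings in the first week, so it cannot support the first time piece of the diary model. Neither analysis separates before from after.

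The label adds to the worry. The plan reports a result for self-focused attention, and in the protocol only the rating scale carries that exact name; the diary is said to monitor attention. If the scale were the outcome, part of the model would be inestimable, and a within-session effect could be diluted by averaging before and after ratings. A reader might then misread one of the two outcomes reported from the multilevel model.

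**Working it through.** The documents give no sample size, power or effect size here, so there is no figure of the plan's own to reproduce. The question is which terms each schedule can support.

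**Inputs.** The visits are one week apart, and the model terms are those in the Data Analysis Plan. Assumed coding: t = days since Visit 1, p1 = min(t, 7), p2 = max(t − 7, 0), C = condition. The linear model has 6 columns: 1, C, p1, p2, C·p1, C·p2. The quadratic model adds p1², p2², C·p1² and C·p2², making 10.

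**Number of ratings.** There is one pair at Visit 2 plus one per home recording. Assuming 6 or 7 home recordings (depending on whether the Visit 3 day counts), this gives 1 + 6 = 7 or 1 + 7 = 8 pairs, that is 14 to 16 ratings per participant.

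**Reading A: the outcome is an evening diary item.** With one row per evening, t = 0 to 13 (or 1 to 14):

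- linear: rank 6 of 6
- quadratic: rank 10 of 10

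Every planned term can be estimated.

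**Reading B: the outcome is the rating scale.** With t = 7 to 13 (or 7 to 14), p1 = 7 in every row. So p1 is 7 times the intercept and C·p1 is 7 times C:

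- linear: rank 4 of 6
- quadratic: rank 6 of 10

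The first-piece slope and its interaction with condition cannot be estimated.

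**Dilution under Reading B.** Take an ATT effect of 1 unit on after-recording ratings only, without noise, and fit 1, C, p2 and C·p2.

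| Layout of the ratings | Constant effect: C | Constant effect: C·p2 | Effect growing 0 to 1: C·p2 (true slope) |
|---|---|---|---|
| Before and after as separate rows | 0.5 | 0.0 | 0.083 (1/6 = 0.167), last day 13; 0.071 (1/7 = 0.143), last day 14 |
| One after-minus-before score per session | 1.0 | 0.0 | 0.167 (0.167); 0.143 (0.143) |

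The halving comes from stacking the two ratings as separate rows, a layout that the plan does not describe. A change score per session recovers both effects without any before/after term.

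**Which reading fits the text.** The sentence naming the outcomes follows the description of the diary model. The variables set aside alongside it (intensity, minutes and frequency of worry) are evidently diary items. The diary covers attention in both weeks, which is what a two-piece time variable needs, and the scale does not. Reading A makes the section coherent, whereas Reading B requires the investigators to have fitted a term with no data.

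**The case for a change.** The strongest case for acting is that a gap remains on either reading. If the outcome is a diary item, the 7 to 8 pairs per participant have no stated analysis. If it is the scale, the model as written does not fit. The name in the outcome sentence matches the scale rather than the diary description, so the document alone does not settle the matter. The remedy would cost a few sentences and at most one model on ratings already scheduled. The plan already separates pre-planned from post-hoc choices, so a labelled addition would suit its practice.

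Part of this stands. The instrument is not named, and the before/after ratings have no written analysis. A within-session result, if reported, would lie outside both analyses described as pre-planned.

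The step from there to a required change does not stand. The documents attach no hypothesis, objective or primary outcome to a within-session contrast, so its importance is supplied by the reader. The scale sits beside the credibility and expectancy questionnaire at Visit 2 and the percentage-of-focus item in Week 2, neither of which has its own analysis. A process or manipulation-check role is plausible, though not stated. That the ratings follow assignment does no evident harm: the first Visit 2 rating precedes both the rationale and the recording and can serve as a pre-exposure value.

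**Conclusion.** No change to the plan is needed. On the natural reading the diary model is estimable in full (6 of 6 columns linear, 10 of 10 quadratic), 0 of the 2 analysed outcomes is affected, and following the plan gives no wrong result. The rank of 4 of 6 (or 6 of 10) arises only if the rating scale was the outcome. The 0.5 and half-slope figures further require before and after ratings to be stacked as separate rows.

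What is left is a gap in description: an unnamed instrument and an ancillary scale without a written analysis. An analyst using these ratings would ordinarily take an after-minus-before score per session, or compare before and after by condition allowing for pairing within session, and would present the result as outside the stated plan. The ANOVA measures and the uncontrollability model are untouched.

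This rests on the outcome sentence referring to diary data and on the assumed day coding; it does not depend on sample size. Evidence that the reported self-focused attention result came from the rating scale would reopen the point.

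### Does the missing SMQ at Visit 3 break the planned three-visit ANOVA of the questionnaires?

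*Combined protocol and SAP*

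**What the plan says.** The Protocol section lists the measures visit by visit.

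- **Visit 1 (Baseline):** "Participants completed consent form, a demographic questionnaire, the GAD-Q-IV, MCQ-30, ACS, PSWQ-PW, SMQ, and the CESD-R".
- **Visit 2 (Preintervention):** "Participants completed the MCQ-30, the ACS, the SMQ, and the PSWQ-PW". The tasks follow, and then the assignment step: "Participants randomly assigned to one of the two conditions: attention training or control".
- **Visit 2, after the recording:** "Participants recomplete the self-focused attention rating scale and the credibility and expectancy questionnaire".
- **Week 2:** the evening diary, a rating of how far the participant focused on the recording, and the attention scale: "Before and after recording, participants completed self-focused attention rating scale".
- **Visit 3 (Postintervention):** "Participants completed the MCQ-30, the ACS, and the PSWQ-PW", followed by the three tasks.

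The Data Analysis Plan then states: "Scores from the questionnaires, the ANT, dot-probe task, and breathing focus task were analyzed using a 3x2 repeated measures" ANOVA, with time as a "variable with three levels (visits 1, 2 and 3) and condition as a variable with two levels (ATT and Control". It does not list the questionnaires that enter the model. Neither the Protocol section nor the Data Analysis Plan gives the SMQ an analysis or a role.

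**The concern.** Four questionnaires in the visit batteries appear at more than one visit: the MCQ-30, ACS, PSWQ-PW and SMQ. The first three are given at all three visits. The SMQ alone drops out at Visit 3. A form given once at baseline reads as a descriptor, but one repeated a week later beside three outcome measures looks like an outcome that lost its final assessment.

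If the SMQ was meant as an outcome, the stated analysis could not be carried out on it. Both scheduled scores precede assignment, so a comparison of conditions would show only chance imbalance and would say nothing about the attention training. The plan calls the ANOVA pre-planned. A reader might therefore ask whether a planned outcome was dropped without comment, collected but left off the list, or never intended as an outcome.

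**Working it through.** The plan states no sample size, power, significance level or effect size that bears on this point, so there is no figure to reproduce. The check is a tally of the schedule against the model.

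**Inputs.** The visit lists in the Protocol section, the position of random assignment within Visit 2, and the ANOVA factors (3 visits, 2 conditions) in the Data Analysis Plan.

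**Step 1: cells filled.** The model has 3 × 2 = 6 visit-by-condition cells. An instrument given at *k* of the three visits fills *k* × 2 of them.

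| Measure | Visits | Cells filled |
|---|---|---|
| MCQ-30, ACS, PSWQ-PW | 1, 2, 3 | 3 × 2 = 6 of 6 |
| Dot-probe, ANT, breathing focus | 1, 2, 3 | 3 × 2 = 6 of 6 |
| SMQ | 1, 2 | 2 × 2 = 4 of 6 |
| GAD-Q-IV, CESD-R, demographic form | 1 | 1 × 2 = 2 of 6 |
| Credibility and expectancy questionnaire | 2 | 1 × 2 = 2 of 6 |

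**Step 2: what the SMQ could support.** The planned time-by-condition interaction has (3 − 1) × (2 − 1) = 2 degrees of freedom. With two visits the SMQ gives (2 − 1) × (2 − 1) = 1, the contrast of Visit 1 with Visit 2. On the listed order of steps, both visits' SMQ scores come before assignment, so 0 of its 2 administrations can carry a treatment effect. The factual part of the concern is therefore correct.

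**Step 3: what the analysis sentence can mean.** Three readings are possible.

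1. *Every questionnaire.* This fails whatever is decided about the SMQ, because the table shows several forms given at a single visit.
2. *Every questionnaire given more than once.* This brings in the SMQ and creates the conflict. The document does not use this category.
3. *Every questionnaire given at all three visits.* This uses the only limit that the plan itself supplies, the three levels of time. It selects the MCQ-30, ACS and PSWQ-PW.

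The third reading yields exactly the Visit 3 list, so schedule and analysis agree without any correction.

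**Step 4: is the SMQ an outcome?** The document states no hypothesis about it, does not name it as an endpoint and reports no analysis of it. Its two administrations bracket the Week 1 monitoring period, which fits use as a pre-intervention measure. The text does not confirm that use, but it does not contradict it either.

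**The case for a change.** The strongest reply is that the third reading repairs the text for its authors. They repeated the SMQ at Visit 2 and gave no reason. Elsewhere in the Data Analysis Plan they do explain such choices: they say which diary variables were analysed, that the choice between uncontrollability and intensity was made post hoc, and why the counts and minutes of worry were left out. The SMQ gets no such explanation. Even if its absence from Visit 3 is only a listing slip, a reader cannot tell whether a post-intervention score exists.

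Part of this stands. The ANOVA questionnaires are not named and the role of the SMQ is not given. The document alone cannot separate an omitted measurement from an omitted word or from a measure never meant as an outcome.

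The step from repetition to intended outcome does not stand, because it is inference and not text. A missing post-randomisation score is a flaw only in a measure on which an effect is to be claimed, and the plan makes no such claim for the SMQ. The 4 of 6 cells and the 1 degree of freedom restate a single fact, its absence at Visit 3. By the same count the GAD-Q-IV and CESD-R have 4 of 6 cells empty, and nobody would call that a defect.

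**Conclusion.** The schedule facts are right, but they do not show that the analysis fails. Under the reading that the time factor imposes, the ANOVA covers three questionnaires and three tasks, each with all 6 cells, and it can be run as written. The diary models do not use the SMQ. No result that the plan sets out to produce is shown to change.

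There is also little to gain from an amendment. The document is in the past tense, so adding the SMQ at Visit 3 appears to be out of reach, and nothing in it shows that the score was needed. The rest is a one-sentence clarification that a sensible analyst already supplies from the visit lists.

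This conclusion rests on two assumptions: that the SMQ was not a treatment outcome, and that the steps of Visit 2 took place in the order listed, which the visit's preintervention label supports. If the SMQ was in fact intended as an outcome and was not collected at Visit 3, the conflict would be real for that one measure, and no treatment effect on it could be claimed. If it was collected and left off the list, the error is clerical. In either case the other measures are untouched.

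### This document analyses at least eight outcomes with no primary outcome, success rule or multiplicity adjustment, and its 3x2 ANOVA names no treatment contrast although two of its three visits precede treatment

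*Combined protocol and SAP*

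**What the plan says.** The Data Analysis Plan covers the visit-level measures in one sentence: "Scores from the questionnaires, the ANT, dot-probe task, and breathing focus task were analyzed using a 3x2 repeated measures Oneway Analysis of Variance (ANOVA"). Time is a "variable with three levels (visits 1, 2 and 3) and condition as a variable with two levels (ATT and Control"). It does not say which effect in this model tests ATT against control, or which score each instrument contributes.

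The Protocol section shows which measures have data at all three visits. At Visit 3, "Participants completed the MCQ-30, the ACS, and the PSWQ-PW" and "Participants completed the dot-probe, the ANT, and the breathing focus task"; all six are also listed at Visits 1 and 2. The SMQ is listed at Visits 1 and 2 only, and the GAD-Q-IV and CESD-R at Visit 1 only, so they cannot enter an analysis with three time levels. The Visit 2 list places the questionnaires and tasks first, and then: "Participants randomly assigned to one of the two conditions: attention training or control".

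For the diary, the Data Analysis Plan uses a piecewise model with one piece before and one after Visit 2. It adds that "Linear multilevel models were run separately for each outcome variable", that "Quadratic models were also run, in case change was not linear", and that "Only uncontrollability of worry and self-focused attention were analyzed".

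No alpha, sample size, primary outcome, success rule, hierarchy or multiplicity adjustment appears in this document.

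**The concern.** Two things are left open.

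- **Which outcome decides.** Eight or more outcomes stand side by side. A reader cannot tell from this document which result determines whether ATT worked, or how a mixture of significant and non-significant results is to be read.
- **Which effect within the ANOVA decides.** A model with three visits and two arms yields a condition main effect, a time-by-condition interaction on 2 degrees of freedom, and several pairwise contrasts. Two of the three visits precede treatment. The main effect averages over visits at which ATT cannot yet have acted. The interaction combines change before randomisation with change after it. Neither is an estimate of the arm difference after the intervention week.

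At stake are how far a significant result can be trusted when it is one of many, and whether the report gives a treatment effect with a confidence interval at all.

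**Working it through.** The document gives no alpha, sample size or power, so there is no figure of its own to reproduce. The outcome count comes from the document. All other inputs are assumptions.

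**1. Outcome count.** Three questionnaires (MCQ-30, ACS, PSWQ-PW) + three tasks (dot-probe, ANT, breathing focus) + two diary items = 8. This is a minimum, because it takes one score per instrument. One ANOVA per score is inferred from the univariate method; separate diary models are stated.

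**2. Chance of at least one false positive.** Assume 5% two-sided per test, no true effects, and a claim made on any one significant result.

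- Independent tests: 1 − 0.95^8 = 1 − 0.663 = 0.337. For the six ANOVA outcomes alone: 1 − 0.95^6 = 0.265.
- Equally correlated test statistics, 400,000 simulated sets of eight: 0.300 at correlation 0.3, 0.251 at 0.5, 0.191 at 0.7, 0.119 at 0.9.
- With a first Holm step of 0.05/8 = 0.00625, the chance is 0.049 for independent tests and 0.031 at correlation 0.7.

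**3. Validity of the interaction.** Simulated under no effect, with 25 or 50 per arm and visit correlation 0.5-0.7, the interaction rejects in 4.9-5.1% of trials when visit correlations are equal. When they decay with time and no sphericity correction is made, it rejects in 5.3-5.6%.

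**4. Power of the candidate tests.** Let the effect be d standard deviations at Visit 3 only, with n per arm and equal visit correlation ρ. The noncentralities are:

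- condition main effect: (d/3)² / [(1+2ρ)/3 · 2/n]
- interaction, 2 df: (2/3)d² / [(1−ρ) · 2/n]
- Visit 3 minus Visit 2 change: d² / [2(1−ρ) · 2/n]
- Visit 3 adjusted for Visits 1 and 2: d² / [v · 2/n], with v = 1 − 2ρ²/(1+ρ)

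Illustration with d = 0.5, n = 30, ρ = 0.7, so that v = 1 − 0.98/1.7 = 0.424:

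| Test | Noncentrality | Power at 0.05 |
|---|---|---|
| Condition main effect | 0.52 | 0.11 |
| Interaction (2 df) | 8.33 | 0.72 |
| Visit 2 to 3 change | 6.25 | 0.69 |
| Adjusted Visit 3 contrast | 8.85 | 0.83 |

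**5. Gain when the interaction has 80% power.** The interaction then needs a noncentrality of 9.94 at 25 per arm or 9.78 at 50. By the formulas in step 4, the ratio of adjusted contrast to interaction is 1.5(1+ρ)/(1+2ρ): 1.125 at ρ = 0.5 and 1.0625 at ρ = 0.7. The adjusted contrast therefore has noncentrality 10.4 to 11.2 on 1 df, which gives 89-91% power at 0.05 and 65-70% at 0.00625. Simulations that also allow decaying correlations widen these ranges to about 87-92% and 62-73%.

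**6. Cost of the Holm step.** 80% power at 0.05 means a noncentrality of 1.960 + 0.842 = 2.80. The critical value at 0.00625 is 2.734, so power is Φ(2.802 − 2.734) = 0.527. With 16 scores in the family, chosen only for illustration, the critical value is 2.955 and power is about 0.44.

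**The case against.** The strongest reply is that the ANOVA is sound. In a time-by-condition design the interaction is the natural treatment test, it holds its error rate, and the text does not exclude follow-up comparisons. This stands. A reader might infer that including pre-randomisation change makes the test biased or invalid; step 3 shows that it does not. Where a real effect exists at Visit 3 only and the interaction has about 80% power, only about 1-4% of significant interactions lack a significant adjusted Visit 3 contrast. The added contrast improves clarity and power; it does not correct an invalid test.

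Secondly, the contrast point does not reach the diary analysis. That model already separates the period before Visit 2 from the period after it and includes a condition-by-time interaction. Running both linear and quadratic forms is a minor matter, because the document does not give the quadratic form from which its effect could be sized.

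Thirdly, the 34% figure needs a rule that any one significant result counts, and no such rule is written. This also stands: the figure describes what follows if the results are read that way. Read outcome by outcome, the error is 5% each.

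Finally, a reader might infer that the trial never had a primary outcome, or that diary items were dropped silently. Neither is supported. This is a short document without an objectives or outcomes section, and a primary outcome may be designated elsewhere. The Data Analysis Plan itself says that uncontrollability was chosen over intensity post hoc and explains why minutes and frequency of worry were set aside.

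**Conclusion.** The concern holds in a limited form. At least eight outcomes are analysed, and this document has no primary outcome, success rule or multiplicity adjustment. For the six visit-level instruments it names no treatment contrast, although two of the three time levels precede treatment. That much follows from the text and needs no assumption beyond one ANOVA per score.

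The sizes do rest on assumptions. The 12-34% chance of a false claim (correlation 0.9 down to independence) requires 5% per test and a claim on any one significant result. The power gain from 80% to about 87-92% requires an effect at Visit 3 only, 25 or 50 per arm and visit correlation 0.5-0.7. The omission limits what may be concluded from the results; it does not invalidate the data or the pre-planned ANOVA.

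**What to change.** 1. **Treatment contrast.** Keep the pre-planned ANOVA in the report. For each visit-level score, add the arm difference at Visit 3 adjusted for the Visit 1 and Visit 2 scores, with its confidence interval. For each diary outcome, report the interaction of condition with the second time piece from the linear model, and use the quadratic model as a sensitivity check of the same quantity.
2. **Multiplicity.** Show Holm-adjusted p-values for these contrasts beside the unadjusted estimates and intervals. Count every score analysed; 0.00625 is the least strict first step possible. Call results that do not survive exploratory.
3. **Disclosure.** State that this document designates no primary outcome, and that the contrasts and the Holm family were set after the analyses were run. They qualify the conclusions and do not restore prospective error control. Holm does not itself name a deciding outcome, and the report should not imply that it does. The disclosure on diary items already in the Data Analysis Plan should be carried into the report.

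The cost is one adjusted regression per visit-level score, some re-reporting and wording; no new data are needed. The price is power: an outcome with 80% at 0.05 has about 53% at 0.00625. A visit-level outcome with 80% on the interaction has about 62-73% at 0.00625 with the adjusted contrast. Both fall further as more scores are counted, and some nominally significant results will become exploratory.

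### The 3x2 repeated-measures ANOVA by default drops randomised participants with a missing visit score and ignores that Visits 1 and 2 precede randomisation; this costs precision and can, under specific dropout patterns, bias the ATT effect.

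*Combined protocol and SAP*

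**What the plan says.** Under Data Analysis Plan, scores from the questionnaires, the ANT, the dot-probe and the breathing focus task go into a "3x2 repeated measures Oneway Analysis of Variance (ANOVA"). Time is a "variable with three levels (visits 1, 2 and 3") and "condition as a variable with two levels (ATT and Control"). The plan calls this analysis pre-planned.

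Under Protocol, Visit 2, the line "Participants randomly assigned to one of the two conditions: attention training or control" comes after that visit's questionnaires and tasks. The only later assessment visit is "Visit 3: Postintervention (1 week after preintervention").

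The diary outcomes are handled differently: "Diary data were analyzed using hierarchical linear modelling", with a random intercept.

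The document gives no sample size, dropout rate, analysis population, missing-data rule or sensitivity analysis for the visit-based outcomes.

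**The concern.** A classical repeated-measures ANOVA needs a score at every level of the time factor. Someone randomised at Visit 2 who does not return has two usable scores, both taken before randomisation, and is still left out. So is someone with a Visit 3 score but an unusable task score at Visit 1 or 2. Unless another rule was applied, the comparison is of completers and not of everyone randomised.

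There is a second inefficiency, which exists even with complete data. Randomisation follows the Visit 1 and Visit 2 assessments, so the arms have equal expected scores at both. The time-by-condition interaction does not use this. It estimates the effect as a difference in change, where conditioning on the two earlier scores would be more precise.

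At stake are power and, under some dropout patterns, the validity of the ATT estimate. The diary model can already use incomplete series, so a method of the needed kind is within the plan.

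**Working it through.** **Inputs.** From the document: three visits, two arms, randomisation after the Visit 2 assessments. Assumed, because nothing is stated: 30 randomised per arm, SD 1 at each visit, correlation 0.6 between any two visits, true effect 0.5 SD at Visit 3, two-sided 5% test. The plan has no figure of its own to reproduce. Power is Φ(0.5/SE − 1.96).

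The ANOVA is represented by the 1-df contrast of Visit 3 against the mean of Visits 1 and 2. The plan does not say which interaction contrast it reads.

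**Complete data.**
- ANOVA contrast: variance per person = 1 + (1 + 0.6)/2 − 2 × 0.6 = 0.60. SE = √(2 × 0.60/30) = 0.200, power 71%.
- Mixed model with equal arm means at Visits 1 and 2: residual variance of Visit 3 given the earlier two = 1 − 2 × 0.36/1.6 = 0.55. SE = √(2 × 0.55/30) = 0.191, power 74%.

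**Missing scores, independent of the data.** The complete-case SE is 0.200/√(fraction complete). The mixed-model SE comes from the expected information over all missing-visit patterns.

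| Pattern | Fraction complete | ANOVA contrast: SE, power | Constrained mixed model: SE, power | Mixed model without the constraint: power |
|---|---|---|---|---|
| 10% at Visit 3 only | 0.90 | 0.211, 66% | 0.202, 70% | 66% |
| 5% at each visit | 0.95³ = 0.857 | 0.216, 64% | 0.198, 71% | 67% |
| 10% at each visit | 0.90³ = 0.729 | 0.234, 57% | 0.205, 68% | 64% |

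The last column separates the two sources of gain. With loss at Visit 3 only, nearly all of it comes from the baseline constraint. With 5% missing at every visit, about half comes from retaining incomplete participants.

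**Bias.** Let Visit 3 be missing for 20%, with log-odds of dropout rising by 1 per SD of the Visit 2 score. Completers then have a mean Visit 2 score of about −0.172 SD. With correlation r, the mean Visit 2 to 3 change among completers is shifted by (1 − r) × 0.172.
- Dependence in one arm only, r = 0.6: 0.4 × 0.172 = 0.07 SD.
- Opposite dependence in the two arms: 2 × 0.07 = 0.14 SD.
- Same dependence and rate in both arms, constant effect: the shifts cancel and bias is zero.

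These figures are for Visit 3 minus Visit 2. Against the mean of Visits 1 and 2 the shift is r − (1 + r)/2 = −(1 − r)/2 per unit, so the bias halves, to about 0.03 and 0.07 SD.

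A separate large simulation with a true effect of −0.40 SD and 20% dropout agrees (change from Visit 2, r = 0.7). The completers' estimate was −0.40 with equal dependence, −0.35 with dependence in the ATT arm only and −0.30 with opposite dependence. With the same slope but 10% against 30% dropout it was −0.35. With equal dropout but an effect changing by −0.2 per SD of Visit 2 score, it was −0.37. A missing-at-random estimate that regressed Visit 3 on the earlier visits separately by arm returned about −0.40 each time.

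**A limit of the remedy.** Separate regressions by arm matter in that last scenario. With one common covariance matrix, the estimate stays at −0.40 + (−0.2)(−0.172) = −0.37. A common matrix does correct dropout that differs between arms when the effect is constant.

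**The case against.** **No loss is documented.** The document reports no missing score and states no exclusion rule. A reader might infer that participants were in fact discarded, or that the diary and visit results rest on different people. The text supports neither: exclusion follows from how the method works by default, and with complete visits both statements would be false. This objection stands, and it is why the sizes are conditional.

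**Worry-related dropout alone is not enough.** A reader might also infer that the ATT effect is biased whenever dropout depends on earlier worry. It is not: the interaction compares changes, and equal dependence in both arms cancels when the effect is constant. Nor does the protocol suggest that dropout would differ between arms. Both arms hear the same rationale, both have a recording, and follow-up is one week.

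**A mixed model recovers little for people lost at Visit 3.** With 14% lost at Visit 3 only, a mixed model without the baseline constraint has 64.5% power against 64.0% for completers. This too stands. There the gain in power comes from baseline adjustment. What the model adds for dropouts is protection against bias under missing-at-random.

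**The ANOVA was pre-planned.** Replacing it after data collection would itself be a post-hoc choice. Reporting the ANOVA alongside, with the new model clearly labelled, meets this.

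**Conclusion.** The concern holds in a limited form. The stated method by default excludes randomised participants with an incomplete visit series, nothing in the plan overrides that, and the method does not use the equality of the arms before randomisation. The precision loss is modest under the assumptions used: 3 percentage points of power with complete data, 4 with 10% lost at Visit 3 only, and 7 with 5% missing at every visit.

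Bias is possible but not shown. It needs dropout rates, or their relation to worry, that differ by arm, or an effect that varies with earlier worry. In the scenarios worked here with 20% dropout and correlation 0.6 it is 0.07 to 0.14 SD for the change from Visit 2, and half that against the mean of the two earlier visits. All sizes rest on assumed sample size, correlation, effect and dropout, and the actual size cannot be judged from the document.

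**What to change.** State the number randomised, the number with a score at each visit by arm, and how incomplete series were handled.

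For outcomes measured at all three visits, estimate the ATT effect as the condition difference at Visit 3 from a linear mixed model. Include all randomised participants by assigned condition, with visit as categorical, unstructured covariance and equal arm means at Visits 1 and 2. Say whether the covariance is common to the arms. If the effect may vary with earlier worry, let it differ by arm, at the price of twelve covariance parameters in place of six.

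Report the pre-planned ANOVA beside it and label the mixed model as added after the original plan. The model cannot be used in this form for the SMQ, which is listed at Visit 2 ("Participants completed the MCQ-30, the ACS, the SMQ, and the PSWQ-PW") but not at Visit 3 ("Participants completed the MCQ-30, the ACS, and the PSWQ-PW"), or for the GAD-Q-IV and CESD-R, listed at Visit 1 only.

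The cost is one re-run on existing data. The downside is small: an extra analysis that was not pre-planned and that relies on missing-at-random.
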